2 End of Treatment assessments (except specimen collection) for patients that terminate treatment early will be done 30 days after the last dose of study drug. A ± 3-day window is allowed.

3 Pregnancy test (by blood) for females of childbearing potential within 30 days prior to enrollment. Serum or urine test on Day 28 and Day 56.

4 Includes anti-viral prophylaxis

5 AEs and SAEs will be reported from randomization until 30 days post last dose. Beginning at 31 days from the last dose of study drug through the end of study follow-up, SAEs deemed to be related to the study drug require reporting, and any unanticipated SAE regardless of relationship to study drug require reporting.

6 Only English- and Spanish-speaking patients are eligible to participate in the Health Quality of Life (HQOL) component of this trial. MDASI surveys to be completed by both English- and Spanish-speaking patients. PROMIS surveys to be completed by English speaking patients only. Surveys may not be completed by surrogates.

7 The Chronic GVHD Provider Survey is due at each Chronic GVHD evaluation and will record GVHD symptoms present in the last week and must be completed by a clinician on the day of the assessment.

Table 4-2 Required and Optional Research Assessments Post-Initiation of Treatment (see APPENDIX B for further details)

Type	Purpose	Day						
		Pre-Therapy ²	0	8	16	24	28	56
Required	Study drug levels ¹	X	X	X	X	X	X	
	Serum Inflammatory Cytokines and GVHD Biomarkers ⁴	X		X			X	X
	Flow Cytometry ⁴	X			X		X	X
Optional (at select centers)	Stool research samples ⁵	X		X			X	X

NOTE: Enrollment is Day 0. First dose of study drug must occur within 12 hours after enrollment and may fall on Day 0 or Day 1.

1 Samples should be drawn just prior to each study drug infusion (and also within 15 to 45 minutes post-end of infusion for the Day 0, 16, 28, and 56 samples).

2 Collect sample prior to administering study drug.

3 Sample should be collected at treatment discontinuation (TD) if that occurs prior to Day 28 (stool)/56 (blood). (Note: This is at the time that patient discontinues the study drug.)

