4.4.4 Required Adverse Event Reporting

4.4.4.1 Non-Serious Adverse Events

All non-serious adverse events will be reported from randomization until 30 days after the last dose of study drug (AAT/PTM). Some anticipated non-serious events will be collected on calendar-driven forms or event-driven forms (Infection, GVHD, Graft Failure, Readmission/Hospitalization, and Progression/Relapse).

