APPENDIX E ANTICIPATED TOXICITIES

The purpose of this appendix is to outline those AEs that commonly occur in the study population. The following is a list of events that the Sponsor considers to be common toxicities for agents used in HCT conditioning and GVHD prophylaxis regimens. The events listed below require reporting via the Toxicity CRF in Advantage eClinical and **do NOT change the reporting obligations, timelines or prevent the need to report an AE meeting the definition of an SAE.**

If aggregate analysis of these events indicates they occur more frequently with study drug, an expedited safety report may be submitted to regulatory agencies.

Lack of relationship to the investigational product is not automatically assumed; therefore, an assessment is required by the Investigator for any events specified below. The Sponsor will also perform the causality assessment on a case-by-case basis and expedite reporting to regulatory agencies when applicable.

General Disorders

Fever

Immune System Disorders

Allergic reaction

GI Disorders

Mucositis

Nausea

Vomiting

Gastric ulcer

Esophagitis

Pancreatitis

GI perforation

Increased appetite

Anorexia

Renal Disorders

Cystitis noninfective

Acute kidney injury

Chronic kidney injury

Hemorrhagic Disorders

Hemorrhage

Blood & Lymphatic Disorders

Leukocytosis

Anemia

Thrombotic thrombocytopenic

purpura/Thrombotic microangiopathy

Hemolytic Uremic Syndrome

Vascular Disorders

Thromboembolic event

Respiratory Disorders

Hypoxia

Dyspnea

Investigations

Neutrophil count decreased

Platelet count decreased

ALT

AST

Bilirubin

Alkaline phosphatase

Hyperglycemia

Hypokalemia

Weight gain

Cardiac Disorders

Hypotension
Hypertension
Cardiac arrhythmia
Left ventricular systolic dysfunction
Pericardial effusion
Restrictive cardiomyopathy

Nervous System Disorders

Restlessness
Insomnia
Glaucoma
Headache
Somnolence
Seizure

Musculoskeletal Disorders

Myopathy
Tendon rupture
Bone fracture
Avascular necrosis
Osteoporosis
Arthralgia

Skin Disorders

Erythema
Rash acneiform

Endocrine/Metabolic Disorders

Cushingoid
Adrenal insufficiency
Edema

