*** Laboratory findings do NOT need to be reported as AEs in the following cases:**

- Laboratory parameters already beyond the reference range at screening, unless a further increase/decrease can be considered an exacerbation of a pre-existing condition.
- Abnormal hematological laboratory parameters considered anticipated due to myeloablative conditioning regimen, or other permitted chemotherapy treatments are not considered AEs.
- An abnormal laboratory value that cannot be confirmed after repeat analysis, preferably in the same laboratory (i.e., the previous result could be marked as not valid and should not necessarily be reported as an AE).

AEs and SAEs will be classified per CTCAE v5.0. All non-serious adverse events will be reported from the time of randomization until 30 days after the last dose of study drug (AAT/PTM). Anticipated non-serious adverse events will be collected on calendar- or event-driven forms. All SAEs are required to be reported from the time of randomization until 30 days following the last dose of study drug. In addition, any SAEs occurring after that 30-day period and assessed as unanticipated or related to the investigational product must be reported. All SAEs are to be followed up until resolved, judged to be no longer clinically significant, or until they become chronic to the extent that they can be fully characterized.

Any unanticipated SAEs from time of enrollment through the study defined follow up are required to be reported following the BMT CTN Administrative MOP Chapter 6. Additionally, any grade 4 anticipated AE not collected on the calendar-driven toxicity or a specified event-driven form must also be reported through the expedited AE reporting system in Advantage eClinical.

Additionally, CSL Behring has a list of events classified as Adverse Events of Special Interest (AESI). These include “anaphylactic infusional reaction” and “suspected transmission of a viral agent via a medicinal product.” Both of these events must be reported through the expedited AE reporting system via Advantage eClinical and must be reported within 24 hours of knowledge of the event even if it does not meet the serious criteria.

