Toxicities are a subset of anticipated adverse events determined to be from the underlying disease process, HSCT, GVHD prophylaxis, or corticosteroid use, and generally, are not considered to be related to the study product. The toxicities listed in Appendix E of the study protocol were pre-determined by the Protocol Team. Once the participant has reached 31 days from the last dose of study drug, toxicities listed in Protocol Appendix E should be reported at the specified time points on the Toxicity CRF.

The primary cause of death will be described for patients that expired on the study.

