7.8.3 SAFETY EVENT SUMMARIES FOR ANALYSIS REPORTS

All safety analyses will be conducted using the safety population. All AEs and SAEs reported on the study will be categorized by MedDRA preferred terms using MedDRA version 23.0 and higher. The number of each type of event and number of patients affected will be described during two study periods: from randomization until 30 days following the last dose of study drug (AAT/PTM), and from 30 days following the last dose until 12 months post-randomization. These events will be reported using the safety analysis population.

In addition, AEs and SAEs will be described in the same manner for the set of patients who received Ruxolitinib or other approved next-line therapy and those who did not. Causes of death for expired participants will be tabulated.

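### SAP 7.8.3 does not say that AE/SAE reporting narrows 30 days after the last dose, and no analysis in the SAP text names the Toxicity CRF that holds late Appendix E toxicities

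*SAP*

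**What the plan says.** **The planned table.** SAP 7.8.3 states: "All AEs and SAEs reported on the study will be categorized by MedDRA preferred terms". Counts of events and of affected patients are then described in the safety population for two periods: randomization to 30 days after the last dose, and "from 30 days following the last dose until 12 months post-randomization". Causes of death are tabulated too.

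**The reporting rule before the boundary.** Protocol Table 4-1, footnote 5: "AEs and SAEs will be reported from randomization until 30 days post last dose". For non-serious events, Protocol 4.4.4.1 says: "All non-serious adverse events will be reported from randomization until 30 days after the last dose of study drug".

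**The rule after it.** SAP 6.5: "any SAEs occurring after that 30-day period and assessed as unanticipated or related to the investigational product must be reported". Protocol 4.4.4.2 says the same and adds Grade 4 anticipated events that neither the toxicity form nor an event form collects. Protocol 4.4.4.3 makes two events of special interest reportable even when not serious, with no end date.

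**Where late anticipated toxicities go.** From 31 days after the last dose, SAP 6.5 says "toxicities listed in Protocol Appendix E should be reported at the specified time points on the Toxicity CRF". Protocol 4.3.2 lists the toxicity time points as Day 120, 6 months and end of treatment.

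**What is said about using them.** Protocol Appendix E: "If aggregate analysis of these events indicates they occur more frequently with study drug, an expedited safety report may be submitted".

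**The concern.** The two periods are presented side by side, but what counts as reportable differs between them. A low count in the second period would partly reflect the narrower rule, and nothing in 7.8.3 warns the reader.

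The events that leave the AE/SAE route are the anticipated toxicities, such as thromboembolic events, kidney injury and avascular necrosis. They continue to be collected, but on a form that SAP 6.5 describes and SAP section 7 does not mention. Causality is judged patient by patient by blinded investigators, and a modest excess of events that are common after transplant is hard to recognise that way. A between-arm comparison is the natural way to look for it, and Appendix E itself contemplates an aggregate look. What is at stake is whether the late safety summary is complete and correctly read. The primary endpoint and the confirmatory hierarchy are not affected.

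**Working it through.** The plan gives no figure to reproduce here. The check sets the collection rules beside the planned analyses and then works out how much follow-up is involved.

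**1. Each kind of late event (from 31 days after the last dose), traced to an analysis in the SAP text**

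| Late event | Route (Protocol 4.4.4, SAP 6.5) | Analysis in SAP text |
|---|---|---|
| SAE judged related, including a serious Appendix E toxicity judged related to AAT | AE/SAE form | 7.8.3, second period |
| Unanticipated SAE | Expedited AE system | 7.8.3, second period |
| Event of special interest | Expedited AE system | 7.8.3, second period |
| Grade 4 anticipated event on no toxicity or event form | Expedited AE system | 7.8.3, second period |
| Death | Death form | Cause of death (7.8.3); NRM and OS (7.5.2, 7.5.3) |
| Appendix E toxicity, non-serious | Toxicity CRF | None that names the form |
| Appendix E toxicity, serious, judged unrelated and anticipated, non-fatal | Toxicity CRF | None that names the form |

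The Grade 4 rule does not rescue the last two rows: it applies only to events not on the toxicity form, and Appendix E terms are on it. The formal AE comparison in SAP 7.5.9 stops 30 days after the last dose.

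**2. Length of the restricted period**

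Inputs: last dose on Day 56 for responders, Day 28 for others (Protocol Table 2-1), or Day 0 if only the first dose is given; a 30-day window; follow-up to Day 365.

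Restricted days = 365 − (last-dose day + 30).

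- Day 56: 365 − 86 = 279 days; 279/365 = 76.4%
- Day 28: 365 − 58 = 307 days; 307/365 = 84.1%
- Day 0: 365 − 30 = 335 days; 335/365 = 91.8%

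**3. What the Toxicity CRF covers**

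The end-of-treatment visit comes 30 days after the last dose for patients who stop early (Table 4-1, footnote 2), so it sits at the boundary. The fixed calendar visits inside the restricted period are Day 120 and 6 months (nominal Day 180). After that no toxicity assessment is scheduled: 365 − 180 = 185 days. That is 185/279 = 66.3%, 185/307 = 60.3% and 185/335 = 55.2% of the three restricted periods.

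**4. Who would be available at 6 months**

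Historical 6-month NRM is 44% for Minnesota high risk (Protocol 1.3.1) and 29% to 44% for the added standard-risk presentations (Protocol Table 1-1). If these applied to 68 patients per arm, before counting deaths after relapse, at most 68 × 0.56 ≈ 38 to 68 × 0.71 ≈ 48 per arm would be alive. A 6-month toxicity percentage is therefore conditional on survival to a material degree.

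**The case against.** The strongest reply is that SAP 7.8.3 is limited to events reported on the study, and SAP 6.5 states the late reporting rule, so a careful reader has what is needed. Moreover, SAP 6.5 defines toxicities as a kind of anticipated adverse event, and Protocol 4.4.1 names the toxicity form among the forms that collect anticipated events. On that reading the second-period table already includes Toxicity CRF entries. This reading is possible, which is why the point is that the comparison is not clearly specified, not that it is excluded. But 7.8.3 does not name the source form, give visit-based denominators or specify a between-arm contrast.

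A reader might infer that any late excess with AAT would vanish from every planned table, or that the second-period table will be almost empty. The documents support neither. Related and unanticipated SAEs enter the table, and unanticipated includes events that differ from the anticipated list in intensity or frequency. Deaths are covered separately. How full the table will be is a prediction. The table shells are in a separate document that was not available, so only the SAP text could be checked.

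Two further replies stand in part. Toxicity goes to the DSMB at each meeting (Protocol 5.3), and the Appendix E review reads as ongoing sponsor surveillance; but SAP 7.8.1 leaves DSMB report content outside the SAP, and neither route puts a comparison in the study report. The AE endpoint ends 30 days after the last dose, about six half-lives at the 5 days in Protocol Table 1-4 (30/5). That justifies the main focus on the earlier window, but it does not explain collecting late toxicities without a stated summary.

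**Conclusion.** The point holds in a limited form. SAP 7.8.3 does not state that its second period rests on a narrower reporting rule, which applies to 76% to 84% of the year for patients whose last dose is Day 56 or Day 28. No analysis in the SAP text names the Toxicity CRF. A late excess of non-fatal Appendix E toxicity that is non-serious, or serious but judged unrelated and anticipated, would not clearly be compared between arms by any analysis the text specifies.

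The number of patients involved cannot be given, because the documents contain no late toxicity rates by arm. The conclusion assumes that the unseen table shells add no toxicity summary; if they do, a sentence in the SAP naming it would settle that part. It would be wrong to conclude that late safety is unmonitored, or that analysing the form would cover the whole late period: no toxicity visit is scheduled from Day 180 to Day 365.

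**What to change.** In SAP 7.8.3:

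1. Title or footnote the second-period table with its restricted reporting rule, and state that its counts are not comparable with those of the first period.
2. Add a by-arm summary of the Toxicity CRF in the safety population at Day 120, 6 months and end of treatment. Give the number and percentage of patients with each Appendix E toxicity and with any, restricted to Grade 3-4 where grade is recorded (the documents do not say whether the form records it). Use patients alive and assessed at that visit as the denominator, show the number of deaths before the visit alongside, and give the risk difference with a 95% CI.
3. State that the form has no scheduled time point after 6 months, so Days 180 to 365 are not covered.
4. State that the table can inform the aggregate review mentioned in Appendix E but does not replace ongoing sponsor or DSMB surveillance.

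Step 1 alone would only be labelling; step 2 supplies the comparison. The cost is one footnote and one descriptive table from a form already in use. The downside is volume: Appendix E lists 54 terms, so three time points give 54 × 3 = 162 term-level intervals with no multiplicity control, all conditional on survival. The table should be labelled descriptive.

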1.6.6 Ruxolitinib for the Treatment of Steroid-Refractory Acute GVHD

The Janus kinase (JAK) and signal transducers and activators of transcription (STAT) signaling pathways play an important role in immune-cell activation and tissue inflammation during acute GVHD. Ruxolitinib is an oral selective inhibitor of JAK1 and JAK2 that reduces the incidence and severity of GVHD *in vivo* while preserving graft-versus-leukemia effects in preclinical models. Recently, ruxolitinib was granted FDA approval in the United States for patients 12 years and older who develop steroid-refractory or dependent acute GVHD grade II-IV based on the results of a prospective phase 2 trial (REACH1). At a protocol-specified dose of 10mg twice daily, 54.9% of the 36 enrolled patients achieved a response on Day 28 without additional therapy. Simultaneously, an open-label, phase 3 trial (based on the same study criteria) was performed outside of the United States with patients randomized to ruxolitinib 10mg twice daily versus best available therapy (BAT). The results on this study were recently published and showed a higher Day 28 and Day 56 response rate in the ruxolitinib arm when compared to BAT (62% vs. 39%; odds ratio, 2.64; 95% C.I. 1.43 to 3.94; P< 0.001) and (40% vs. 22%; odds ratio 2.38; 95% C.I. 1.43 to 3.94; P< 0.001), respectively. Adverse events were not significantly different between the study arms with thrombocytopenia, anemia and CMV infection being most common.

The availability of an FDA-approved agent for patients enrolled onto this trial may affect the frequency and timing of use of next-line therapy. Importantly, while the results of the REACH 1 and 2 trials are encouraging, a majority of patients will not achieve or maintain a response through Day 56 of treatment with ruxolitinib and outcomes remain poor for patients with steroid-refractory acute GVHD. In an effort to improve upon the outcomes seen thus far with ruxolitinib in a steroid-refractory setting, patients that progress or are non-responders on the current trial will have the option to stay on AAT/PTM when next-line therapy with ruxolitinib is initiated. These patients will be followed for secondary endpoints (while being considered a failure for the primary endpoint). Importantly, the wealth of experience with AAT outside of the study indication would suggest that AAT is unlikely to have drug interaction with ruxolitinib nor contribute additional safety concerns.

CHAPTER 2

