5.7.6 Proportion of Response (Next-Line Therapy)

The proportions of patients with CR, PR (including subset with VGPR), and treatment failure (TF) at Days 7, 14, 21, 28, 56, and 86 post-randomization who receive ruxolitinib or other next-line therapies approved by the protocol Chairs as next-line therapy and remain on AAT/PTM will be described and compared between the treatment groups, to evaluate any differences in safety and efficacy, using the chi-square test or Fisher’s exact test as appropriate. The proportion of AE/SAE will be described in these patient populations.

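### SAP 7.8.3 groups adverse events by ever having received approved next-line therapy and drops Protocol 5.7.6's stay-on-study-drug condition, so its table cannot isolate events on AAT/PTM plus next-line therapy

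*SAP*

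**What the plan says.** SAP 7.8.3 counts events and affected patients in two reporting periods, as follows: "from randomization until 30 days following the last dose of study drug (AAT/PTM), and from 30 days following the last dose until 12 months post-randomization". On next-line treatment it then says "AEs and SAEs will be described in the same manner for the set of patients who received Ruxolitinib or other approved next-line therapy", with everyone else as the second group. That sentence names neither the treatment arms nor the next-line start date, and does not ask whether the patient was still receiving study drug.

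Protocol 5.7.6 defines its group differently. Response proportions in patients who receive ruxolitinib or another Chair-approved drug "as next-line therapy and remain on AAT/PTM will be described and compared between the treatment groups, to evaluate any differences in safety and efficacy". It adds: "The proportion of AE/SAE will be described in these patient populations".

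The exposure at issue comes from the protocol itself. Sections 2.5.1.10 and 2.5.3.3 encourage patients who start ruxolitinib to continue study drug, and section 1.6.6 argues from experience in other indications that "AAT is unlikely to have drug interaction with ruxolitinib nor contribute additional safety concerns".

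SAP 7.11 names one change from the protocol analysis, the significance level for exploratory endpoints. This one is not listed.

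**The concern.** Having ever received ruxolitinib is not the same as having received it together with AAT or placebo. Protocol 2.5.3.3 lets the physician stop study drug when ruxolitinib is given. Section 2.5.1.7 ends study drug at Day 28 for patients not in response. SAP 7.2.2 expects some next-line starts at or after Day 28. The next-line set therefore contains patients with little or no overlap of the two treatments. For every patient in it, events from before the start are also counted.

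The comparator has a similar problem. Read literally, the patients who did not receive approved next-line therapy include those given an unapproved one, which Protocol 2.5.3.3 foresees, next to patients who never needed more treatment.

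At stake is the one descriptive table in the SAP that bears on the safety of the combination. A real difference between arms could be diluted, or an apparent one could arise from time before exposure. The primary endpoint is not affected.

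**Working it through.** **Texts side by side**

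| Feature | Protocol 5.7.6 | SAP 7.8.3 |
|---|---|---|
| Next-line drug | Ruxolitinib or Chair-approved | Same |
| Must stay on AAT/PTM | Yes | No |
| Between arms | Yes, for safety and efficacy | Arms not named |
| Events tied to next-line start | No | No |

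No other SAP section supplies the missing condition. SAP 7.5.7 is the counterpart of Protocol 5.7.6 but covers response only, and SAP 6.3.7 places that endpoint in the full ITT population. SAP 3.3 keeps the stay-on-study-drug wording in secondary objective 6, but no analysis in the SAP applies it to adverse events.

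**How much of the counted time is off target**

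The plan states no figure to reproduce, so this is an illustration. Let s be the day next-line therapy starts and L the day of the last study drug dose. The first period in SAP 7.8.3 runs from Day 0 to L + 30.

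- Share before next-line start = min(s, L + 30) / (L + 30)
- Share between next-line start and last dose = max(0, L − s) / (L + 30)
- Share after both = max(0, L + 30 − max(s, L)) / (L + 30)

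Inputs from the documents: the earliest start is 72 hours for progression and Day 7 for non-response (Protocol Table 2-3). The last scheduled dose is Day 28 for non-responders and Day 56 for Day 28 responders, including those on study drug plus ruxolitinib (Protocol 2.5.1.7). The pairings of s and L are assumptions.

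| s | L | Period ends | Before start | Start to last dose | After both |
|---|---|---|---|---|---|
| 3 | 56 | 86 | 3/86 = 3% | 53/86 = 62% | 30/86 = 35% |
| 3 | 28 | 58 | 3/58 = 5% | 25/58 = 43% | 30/58 = 52% |
| 7 | 28 | 58 | 7/58 = 12% | 21/58 = 36% | 52% |
| 14 | 28 | 58 | 14/58 = 24% | 14/58 = 24% | 52% |
| 28 | 28 | 58 | 28/58 = 48% | 0% | 52% |
| 28 | 56 | 86 | 28/86 = 33% | 28/86 = 33% | 35% |
| 7 | 8 | 38 | 7/38 = 18% | 1/38 = 3% | 30/38 = 79% |
| 60 | 56 | 86 | 60/86 = 70% | 0% | 26/86 = 30% |
| 90 | 56 | 86 | 100% | 0% | 0% |

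Under a constant event rate these shares are also the expected shares of the events counted in the first period. The Day 3 rows are the extreme: Protocol 2.5.3.3 also expects two doses before next-line therapy for progression, so the second infusion would have to fall early in its ±3-day window.

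A patient who starts after the first period adds few later events to offset this. From 31 days after the last dose, only SAEs that are related or unanticipated have to be reported (Protocol 4.4.4.2 and Table 4-1, note 5).

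**The case against.** A reader might infer that the SAP counts pre-start events as next-line events, or that the combination safety question goes unanswered. The documents support neither. SAP 7.8.3 describes events in a set of patients and does not attribute them to next-line therapy. It tabulates events more than 30 days after the last dose separately. The commitment in Protocol 5.7.6 still stands, and the safety population is classified by treatment received (SAP 5.3), so a display by arm is possible. The table shells, which were not available for this review, may add onset windows.

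Nor is the missing start-date anchor a departure from the protocol, since Protocol 5.7.6 has none either. Anchoring is a better method; the dropped condition is the departure. The split is descriptive, with no test or decision attached.

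Stopping infusions does not end exposure at once. Protocol Table 1-4 gives a terminal half-life of about 5 days in AAT-deficient subjects, and Protocol 1.6.3 notes that stool losses raise clearance in lower GI GVHD. It would be too strong to say that everyone who had stopped had no combined exposure.

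Finally, infections are not reported as AEs or SAEs (Protocol 4.4.1, SAP 6.5), although Protocol 1.6.6 names CMV infection among the commonest events in the ruxolitinib trial. No AE table can give the full safety picture.

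These points limit the claim and shape the remedy. They do not restore the dropped condition. SAP 7.1 describes the shells as format specifications, and population and onset rules belong in the SAP.

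**Conclusion.** The point holds in a limited form. As written, SAP 7.8.3 cannot isolate events on AAT/PTM plus next-line therapy. It drops a condition that Protocol 5.7.6 sets, without declaring it in SAP 7.11, and its comparator is mixed.

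The share of the first period that precedes next-line start is about 3% to 48% for starts up to Day 28 with a last dose on Day 28 or Day 56, apart from early stopping of study drug. It rises to 100% when the start comes after that period. This rests on assumed start and last-dose days and a constant event rate. The documents give no distribution of start times, so no average can be stated.

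The weakness is in a descriptive safety summary. It should be corrected, but it does not bear on the primary result.

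**What to change.** Keep the existing table and add to SAP 7.8.3, by arm:

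- AEs and SAEs with onset on or after the first approved next-line dose, through 30 days after the last study drug dose, in patients whose study drug was not recorded as discontinued when next-line therapy began. Do not require a later infusion: that would exclude a patient who died or had an SAE before the next one was due.
- A separate row for post-start events in patients who had already stopped AAT/PTM, so that no event is lost.
- Patients on unapproved next-line therapy shown separately.
- Any event rates limited to the full-reporting window, which ends 30 days after the last dose.

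Reconcile the text with Protocol 5.7.6 and list any remaining departure in SAP 7.11.

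No new data are needed. Infusions are recorded in the eCRF (Protocol 2.5.1.5), second-line therapy is recorded repeatedly (Protocol 4.3.2), and its initiation date is already used for duration of response (SAP 6.3.1). SAP section 1 allows revision before the database hard lock. The cost is SAP wording and a few more descriptive tables, some with small numbers.
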